10.4.1 Analysis of Mean Changes for Vital Sign and Weight

Diastolic blood pressure, systolic blood pressure and pulse will be analyzed separately for each position of measurement. Analyses of mean change from baseline to each double blinded visit value and to the minimum, maximum and final double-blind value will be presented for each vital sign and weight variable. Analysis of orthostatic SBP, DBP and pulse rate will be conducted similarly.

10.4.2 Potentially Clinically Significant Vital Sign and Weight Values

Criteria for potentially clinically significant values have been predefined for selected vital sign and weight variables as outlined in Appendix. For each variable, a summary of the number and percentage of subjects in each treatment group who have at least one double blind observation that meets the PCS criteria and is more extreme than their baseline value will be provided. A listing will also be prepared that will include, for each variable, all observations for each subject that met the PCS criteria for that variable at any time during the study.

10.5 Analysis of Electrocardiogram (ECG) Variables

Electrocardiogram (ECG) variables include: heart rate (HR), PR interval, QRS interval, uncorrected QT interval, and QT interval corrected for heart rate using Fridericia's

formula (QTcF). Analyses of ECG variables will be performed on the Stand-Alone data set.

10.5.1 Analysis of Mean Changes for ECG

Analyses of mean change from baseline to each double-blind visit value and to the minimum, maximum and final double-blind value will be presented for each ECG variable. Analyses of mean change from final double-blind value to final post-treatment value will also be presented for each ECG variable.

10.5.2 Potentially Clinically Significant ECG Values

Criteria for potentially clinically significant values have been predefined for selected ECG variables as outlined in [Appendix C](#). For each variable, a summary of the number and percentage of subjects in each treatment group who have at least one double-blind observation that meets the PCS criteria and is more extreme than their baseline value will be provided. Listings will also be prepared to include all observations for each variable for each subject that met the PCS criteria for that variable at any time during the study. No comparisons of treatment groups will be performed.

10.6 Analysis for Other Safety Variables

10.6.1 Analysis of Columbia-Suicide Severity Rating Scale (C-SSRS)

Analyses of C-SSRS will be performed on the Stand-Alone data set.

Number and percentage of subjects in the following categories will be summarized for each treatment group and overall subjects by visit and for the entire study:

- Answered 'Yes' to each C-SSRS item
- Had suicidal ideation (defined as answering 'Yes' to one or more suicidal ideation items)
- Had suicidal ideation only (defined as answering 'Yes' to one or more suicidal ideation items and answering 'No' to all suicidal behavior items)

- Had suicidal behavior (defined as answering 'Yes' to one or more suicidal behavior items)
- Had suicidal ideation or behavior (defined as answering 'Yes' to one or more suicidal ideation or behavior items)

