RBANS	25	S				6					6					6										
CTT Parts 1 & 2	5 – 10	S				7					7					7										
Letter Fluency Test (wpm)	1	S				8					8					8										
NNIPPS-PPS ^d	30 – 45	S and SP				9					9					9										
PGI-C ^e	1 – 2	S	X	X	X	X	X	X	X	X	X	X	X	X	X	X	X	X	X	X	X	X	X	X	X	X
EQ-5D ^e	8	S	X	X	X	X	X	X	X	X	X	X	X	X	X	X	X	X	X	X	X	X	X	X	X	X
C-SSRS (at every visit) ^f	<5	S	X	X	X	X	X	X	X	X	X	X	X	X	X	X	X	X	X	X	X	X	X	X	X	X
BioStamp nPoint ^g		S	X	X	X	X	X	X	X	X	X	X	X	X	X	X	X	X	X	X	X	X	X	X	X	X
PSP Caregiver Questionnaires	25	SP	X	X	X	X	X	X	X	X	X	X	X	X	X	X	X	X	X	X	X	X	X	X	X	X
TSQM-9	5	S	X	X	X	X	X	X	X	X	X	X	X	X	X	X	X	X	X	X	X	X	X	X	X	X

Table 3. Diagnostic Tools and Scale Order, and Duration of Administration (Continued)

Approx = approximately; CGI-C = Clinical Global Impression of Change; CGI-S = Clinical Global Impression of Severity; C-SSRS = Columbia-Suicide Severity Rating Scale; CTT = Color Trails Test; D/C = discontinuation; EQ-5D = EuroQol-5D; F/U = follow-up; min = minutes; NNIPPS-PPS = National Institute of Neurological Disorders and the Society for Progressive Supranuclear Palsy; PGI-C = Patient Global Impression of Change; RBANS = Repeatable Battery for Assessment of Neuropsychological Status; S = subject; SEADL = Schwab and England Activities of Daily Living Scale; SP = study partner; TSQM-9 = Treatment Satisfaction Questionnaire for Medication; UPDRS = Unified Parkinson's Disease Rating Scale; Wk = week; wpm = words per minute

- a. Numbering listed in the table provides a pre-defined order of administration that should occur during each visit.
- b. Audio recordings/central review of the administration/assessment of selected scales may be conducted.
- c. Assess prior to randomization and the first dose of study drug.
- d. The NNIPPS-PPS will not be administered in Japan.
- e. Scale may be administered/assessed at any time during the visit, after the other procedures are completed, with the exception of the scheduled infusion time.
- f. Scale may be administered/assessed at any time during the visit with the exception of the scheduled infusion time.
- g. BioStamp nPoint will also be administered at Weeks 4 and 8.

The diagnostic tools and rating scales are as follows:

PSP Rating Scale¹²

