8.1.2.6 Analysis of C-SSRS

The number and percentage of subjects in the following categories will be summarized for each treatment group by visit and for the entire study:

- Answered 'Yes' to each C-SSRS item
- Had suicidal ideation (defined as answering 'Yes' to one or more suicidal ideation items)
- Had suicidal ideation only (defined as answering 'Yes' to one or more suicidal ideation items and answering 'No' to all suicidal behavior items)
- Had suicidal behavior (defined as answering 'Yes' to one or more suicidal behavior items)
- Had suicidal ideation or behavior (defined as answering 'Yes' to one or more suicidal ideation or behavior items).

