5.0 Analysis Populations

5.1 Analysis Data Sets

Data Sets for Efficacy Analyses

Two data sets will be created for the efficacy analysis: an intent-to-treat (ITT) data set and a delayed-start data set.

ITT Data Set: the ITT data set consists of all subjects who received any dose of study drug in Study M15-563. All efficacy analyses will be conducted on the ITT data set using data from Study M15-563 alone unless otherwise specified.

Delayed-Start Data Set: The Delayed-Start data set includes all subjects from the Study M15-562 ITT data set who received placebo or ABBV-8E12 in Study M15-562 regardless of whether they enroll in Study M15-563 or not. For the Delayed-Start analysis, efficacy data for PSPRS total score from both Study M15-562 and Study M15-563 studies will be included.

Data Sets for Safety Analyses

The safety data set will consist of all subjects who received any dose of study drug infusion in Study M15-563. For safety analyses, the actual treatment received will be used instead of the treatment assignment at enrollment. There are two safety data sets: a Stand-Alone data set and a Cumulative data set.

Stand-Alone Data Set: The Stand-Alone data set is the primary data set for safety analyses, and will contain data from Study M15-563 only, regardless of the treatment received in Study M15-562. Baseline for the Stand-Alone data set will be the last observation on or before the first dose of ABBV-8E12 in Study M15-563. If no Baseline is recorded in Study M15-563, the last value in Study M15-562 will be used as the Baseline.

Cumulative Data Set: The Cumulative data set will consist of data from both Study M15-562 and Study M15-563. It is the secondary data set for safety analyses. For subjects who were in the placebo group in Study M15-562, their safety data from Study M15-562 will not be included in the Cumulative data set but their safety data from Study M15-563 will be included. For subjects who were in the placebo group in Study M15-562, Baseline will be the last observation prior to the first dose of study drug in Study M15-563. For subjects who were in ABBV-8E12 treatment groups in Study M15-562, Baseline for the Cumulative data set will be their Baseline in Study M15-562.

Data Sets for Biomarker Analyses

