10.3.3 Potentially Clinically Significant Laboratory Values

Criteria for potentially clinically significant (PCS) values have been predefined for selected laboratory variables as outlined in [Appendix A](#). For each variable, a summary of the number and percentage of subjects in each treatment group who have at least one double-blind observation that meets the PCS criteria and is more extreme than their baseline value will be provided. A listing will also be prepared that will include, for each variable, all observations for each subject that met the PCS criteria for that variable at any time during the study.

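### The overall C-SSRS percentages have no defined period and no baseline comparison, so they cannot separate pre-existing from new or worsened suicidal ideation or behavior

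*SAP*

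**What the plan says.** SAP 10.6.1 states that "Analyses of C-SSRS will be performed on the Stand-Alone data set". It lists five categories: a yes to each item, ideation, ideation only, behavior, and ideation or behavior. The number and percentage of subjects in these categories "will be summarized for each treatment group and overall subjects by visit and for the entire study". Protocol 8.1.2.6 lists the same categories, which "will be summarized for each treatment group by visit and for the entire study". Neither section mentions baseline or a starting point for the overall period.

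SAP 5.1 says that the Stand-Alone set "will contain data from Study M15-563 only, regardless of the treatment received in Study M15-562". It also defines a baseline: "Baseline for the Stand-Alone data set will be the last observation on or before the first dose of ABBV-8E12 in Study M15-563". If M15-563 has no baseline record, the last M15-562 value is used.

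In Protocol Table 3 the scale's row label begins "C-SSRS (at every visit", and Day 1 is a scheduled visit. Footnote c, on the Day 1 column, reads "Assess prior to randomization and the first dose of study drug". Footnote f, on the C-SSRS row, and Appendix C footnote m allow the scale at any point in the visit outside the infusion.

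Elsewhere the SAP does use baseline. A laboratory value is counted as potentially clinically significant only if it "meets the PCS criteria and is more extreme than their baseline value" (SAP 10.3.3). SAP 10.4.2 and 10.5.2 apply the same condition to vital signs, weight and ECG. SAP 10.2 restricts treatment-emergent adverse events to those that start or worsen from the first dose date onward.

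**The concern.** In M15-563 every subject receives ABBV-8E12 and there is no concurrent placebo arm. Comparison with the subject's own pre-dose state is then the main way to read a suicidality percentage. A raw count of subjects who ever answered yes does not give that comparison.

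Some carry-in is possible. Protocol 5.3.1.1.13 excludes subjects who report ideation with plan on Day 1, but it does not exclude milder ideation. Such a subject could appear in the overall row with no change after the first M15-563 infusion.

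At stake is whether a reader of the study report can tell how many subjects developed ideation or behavior, or got worse, during M15-563. SAP 4.4 also lists a C-SSRS summary among the DMC's interim safety outputs. The open definition also lets two programmers produce different tables from the same text.

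**Working it through.** The documents state no C-SSRS rate, test or power figure, so there is no planned figure to reproduce. The check is a comparison of rules, followed by a counting identity.

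**1. Rules side by side**

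| Safety output | Where | Link to the pre-dose state |
|---|---|---|
| Potentially clinically significant laboratory values | SAP 10.3.3 | Must be more extreme than baseline |
| Vital signs and weight, ECG | SAP 10.4.2, 10.5.2 | Same |
| Treatment-emergent adverse events | SAP 10.2 | Must start or worsen from the first dose date |
| Laboratory shifts | SAP 10.3.2 | Conditioned on baseline category |
| C-SSRS | SAP 10.6.1 | None stated |

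The general window in SAP 10.1 does not help. It sets limits after the last dose (45 days, 20 weeks) but none at the first dose.

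**2. Which Day 1 record?** Under SAP 4.2, when the dosing gap is no more than 45 days, the M15-562 Week 52 assessments serve as Day 1. Protocol 5.1 says they need not be repeated. With a gap of more than 45 days but less than 8 weeks, Day 1 procedures must be done. The Stand-Alone set holds M15-563 data only. The overall row could therefore include pre-dose answers for longer-gap subjects and omit them for the others.

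**3. Can the by-visit rows recover the answer?** No, because they do not link subjects. If 5% are positive on Day 1 and 5% at a later visit (assumed figures), the newly positive share at that visit may be anything from 0% (the same subjects) to 5% (all different).

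**4. Counting identity.** Let pb be the share positive on Day 1, q the share of the remainder who become positive after the first infusion, and s the share of Day 1 positives who answer yes again later. Worsening among Day 1 positives is left out.

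- Overall row including Day 1: pb + (1 − pb)q
- Overall row, post-dose assessments only: pb·s + (1 − pb)q
- New onset: (1 − pb)q

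The excess over new onset is pb if Day 1 counts, and pb·s if only post-dose assessments count. An illustration with q = 5% and s = 50% follows; pb, q and s are all assumptions.

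| pb | Including Day 1 | Post-dose only | New onset |
|---|---|---|---|
| 1% | 1 + 0.99×5 = 5.95% | 0.5 + 4.95 = 5.45% | 4.95% |
| 5% | 5 + 0.95×5 = 9.75% | 2.5 + 4.75 = 7.25% | 4.75% |
| 10% | 10 + 0.90×5 = 14.50% | 5 + 4.50 = 9.50% | 4.50% |

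With pb = 5%, taking s as 30%, 50% or 80% gives 6.25%, 7.25% or 8.75% for the post-dose-only row, against 4.75% new onset. Dropping Day 1 therefore removes only pb(1 − s). Ideation that persists is recorded again at later visits, so a comparison with baseline is needed as well.

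**The case against.** A reader might infer that the plan takes ideation recorded before the first M15-563 infusion and reports it as caused by, or arising on, ABBV-8E12. The documents do not support that reading, for four reasons.

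- The overall period is undefined. Including Day 1 is the natural reading, but it is an inference, and a programmer could equally restrict the row to post-baseline records. The Day 1 record may also be an M15-562 Week 52 record.
- No category is labelled new or treatment-emergent. The table is descriptive, and SAP 10.1 plans no comparison between groups. Suicidality reported as an adverse event is covered by the treatment-emergent rule in SAP 10.2.
- The 2000/2000 mg and 4000/4000 mg groups were already on ABBV-8E12 in M15-562, so their ideation at M15-563 entry may itself have arisen on drug.
- Day 1 is a scheduled visit, so the by-visit summary can already show it. The Day 1 exclusion of ideation with plan limits carried-in ideation to less severe forms.

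The timing of the Day 1 interview is also not secure. Table 3 footnote c places it before the first dose, while footnote f and Appendix C footnote m allow any time outside the infusion.

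All of this stands, and it limits the point. It does not supply the missing comparison: however the period is programmed, persistent and new ideation fall in the same count.

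**Conclusion.** SAP 10.6.1 and Protocol 8.1.2.6 define neither the overall period nor a baseline comparison. The overall percentages therefore cannot separate pre-existing from new or worsened ideation or behavior, although the SAP makes that separation for its other main safety outputs. This rests on the text alone and needs no assumed rate.

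The possible misattribution to ABBV-8E12 is clear only for the placebo/2000 mg and placebo/4000 mg groups, whose pre-infusion answers precede any ABBV-8E12. A reader might extend it to all four groups; the early-start groups' exposure in M15-562 rules that out.

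The size cannot be given as a percentage or a multiple, because the documents contain no C-SSRS rate. The tabulated values only show the mechanism: an excess of 1 to 10 percentage points for an assumed Day 1 prevalence of 1% to 10% if Day 1 counts, and less if it does not. Severity is minor. The change is still worthwhile, because a new-or-worsened count is more informative than an ever-yes count and uses data already collected.

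**What to change.** Amend SAP 10.6.1 as follows.

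1. Define the overall period as assessments after the first M15-563 infusion, and say whether it includes the follow-up window in SAP 10.1.
2. Report the SAP 5.1 Stand-Alone baseline as its own column. State that the last M15-562 value is used when M15-563 has no baseline record, including when Week 52 serves as Day 1.
3. Add, by treatment group and overall, the number and percentage of subjects with new or more severe ideation or behavior compared with that baseline, and state how more severe is determined.
4. Footnote the table: for 2000/2000 mg and 4000/4000 mg subjects this baseline was taken on ABBV-8E12, so ideation that arose in M15-562 counts as baseline.

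Reconcile Protocol Table 3 footnote c with Table 3 footnote f and Appendix C footnote m, so that the order of the Day 1 interview and the first infusion is unambiguous.

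The cost is a few sentences and one extra table block. No new data are needed, and no planned by-visit output is lost. The one downside is the early-start limitation in item 4.

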10.6.2 Summary of MRI Safety Evaluations

MRI safety evaluations will be summarized by treatment group based on MRI evaluations in the double blinded period. The summaries include the number and percentage of subjects pertaining cerebral edema, micro- and macro-haemorrhages, white matter hyperintensities (ARWMC score) across visits; number and percentage of subjects with presence and increasing severity of cerebral edema; number and percentage of subjects with new micro- and macro-haemorrhage lesions; number and percentage of subject with white matter hyperintensities change (ARWMC score) from previous time point. Descriptive statistics (mean, median, minimum, maximum) of number of new micro- and macro-hemorrhages or new lesions, as well as changes in ARWMC score in the double-blinded period will be presented.

11.0 Pharmacokinetic Analysis

For ABBV-8E12 serum and/or CSF concentration data, descriptive statistics will be provided for each scheduled time of measurement with a breakdown by groups defined by treatment in Study M15-562 and treatment in this study.

12.0 Analysis of Biomarker Research Variables

12.1 Descriptive Statistics

For CSF and plasma concentrations of tau and volumetric MRI variables, descriptive statistics will be provided for each scheduled time of measurement for each treatment group. The descriptive statistics will be provided for the baseline measurement also. The data set for which the descriptive statistics will be provided is described in Section 5.1 under the heading "Data Sets for Biomarker Analyses." The four treatment groups are

those defined in the first paragraph of Section 4.2. That is, the treatments of the 4 groups are:

- Subjects who received ABBV-8E12 2000 mg in Study M15-562 and continue on the same dose in Study M15-563
- Subjects who received ABBV-8E12 4000 mg in Study M15-562 and continue on the same dose in Study M15-563
- Subjects who received placebo in Study M15-562 and receive ABBV-8E12 2000 mg doses in Study M15-563
- Subjects who received placebo in Study M15-562 and receive ABBV-8E12 4000 mg doses in Study M15-563

The descriptive statistics for a post-baseline time will be provided for both the data of the given time and the changes from baseline.

Time of measurement will be indicated for two different reference points. The first reference point will simply be the day of the first dose of Study M15-563. The second reference point is the time relative to the first dose of ABBV-8E12, which will be the first dose of Study M15-562 or the first dose in Study M15-563, depending upon whether the subject was administered ABBV-8E12 or placebo in Study M15-562. For subjects who were treated with ABBV-8E12 in Study M15-562, the time relative to the second reference point will be 52 weeks longer than the time relative to the first reference point. For the subjects whose treatment in Study M15-562 was placebo, the time relative to both reference points will be the same.

The statistics will consist of: number of observations (n), mean, standard deviation, coefficient of variation as a percentage (quotient of standard deviation and mean, multiplied by 100), minimum, median and maximum. If the logarithmic transformation is employed for a variable in the statistical analysis that is described in Section 12.2, the geometric mean will also be reported. All of these descriptive statistics except for the coefficient of variation and the geometric mean will be provided for the change from baseline at each scheduled time of measurement in Study M15-563.

12.2 Analysis on Treatment by ABBV-8E12 for at Least One Year

The data set on which this analysis will be performed is the Longer-Term Biomarker Data Set described in Section 5.1. All the measurements in this data set were obtained after a subject was on treatment with ABBV-8E12 for 52 weeks or longer.

Transformation of Variables for Analysis

If the probability distribution for a variable appears to have considerable non-symmetry (e.g., skewness coefficient > 1.00 in magnitude), a transformation will be sought that has an approximately normal distribution. If a transformation is employed, estimates of central values on the original scale (back transformation of SAS least squares means) will be provided. If the logarithmic transformation is used, the comparison of the treatments will be in terms of the ratio of central values.

Analysis of CSF and Plasma Concentration Variables

For CSF and plasma concentrations of tau, an MMRM analysis will be performed to compare the effects of the 2000 and 4000 mg doses of ABBV-8E12. The model will include classification by ABBV-8E12 dose and time of measurement. There will be an effect for the interaction of ABBV-8E12 dose and time of measurement. The subjects in each treatment group will be viewed as a random sample. The baseline value will be a covariate. The model will also initially have a term for the interaction of baseline value and visit.

After the structure of the covariance matrix is decided upon, as discussed below, a test will be performed on the term for the interaction of baseline value and visit. The term for this interaction will be removed from the model if the statistic is not significant at level 0.100.

Within the framework of the final model, the mean across the scheduled times of measurement will be estimated for each ABBV-8E12 dose level. The hypothesis of no difference between the main effects of the two ABBV-8E12 dose levels (i.e., a composite

assessment for the several times of times of evaluation) will be tested at significance level 0.050. The SAS least squares means (LS means) for the two ABBV-8E12 dose levels across time will be provided and presented graphically.

There will be three candidates for the structure of the covariance matrix for the conditional distribution of the vector of scheduled responses, given the values of the covariate(s). The simplest model will be the compound symmetry model (SAS option CS with the REPEATED statement), and another option will be the one that imposes no conditions on the covariance matrix (SAS option UN with the REPEATED statement). The third model will allow the variances for the several times of response to differ, but impose the condition that all pairs of the response variables have the same correlation coefficient (SAS option CSH with the REPEATED statement). An approximate test will be performed to compare the model with no restrictions to the compound symmetry model, with a multivariate normal distribution assumed for the conditional distribution. Such a test will also be performed to compare the model of intermediate complexity (SAS CSH option) to the compound symmetry model. The approximate test will be that based upon the difference in the values of $-2\log(\text{likelihood})$ for the two models, using the chi-square approximation for the null distribution, with degrees of freedom being the difference in the number of parameters required for the two structures of the covariance matrix. If the test statistic is not significant at level 0.050 for either test, the compound symmetry model will be used. If the statistic is significant at level 0.050 for one of the two tests, the compound symmetry model will not be used, and the two more complex models will be compared using the approximate test. If the statistic for this test is significant at level 0.050, the model with no restrictions will be used. Otherwise, the model of intermediate complexity will be used.

Analysis of Imaging Variables

For imaging variables, an MMRM analysis corresponding to that described for the tau variables will be performed. However, for the volumetric MRI variables, there will be two covariates. In addition to the baseline value, a variable reflecting head size

(e.g., intracranial volume) will be a covariate. For this second covariate, interaction with visit will not be included in the model.

For other variables for which data are reported, descriptive statistics will be provided, and appropriate analyses will be performed.

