4.0 Study Objectives, Design and Procedures

4.1 Objectives

The primary objectives of this study are:

- To assess the long-term safety and tolerability of ABBV-8E12 in subjects with progressive supranuclear palsy (PSP).
- To assess the long-term efficacy of ABBV-8E12 in slowing disease progression in subjects with PSP as measured by the PSP Rating Scale (PSPRS).

The secondary objectives of this study are:

- To assess the long-term efficacy of ABBV-8E12 in slowing disease progression and functional impairment in subjects with PSP as measured by secondary endpoints.
- To assess the pharmacokinetics of ABBV-8E12 in subjects with PSP.

- To assess the long-term efficacy of ABBV-8E12 in slowing regional and/or whole brain atrophy in subjects with PSP as measured by volumetric magnetic resonance imaging (MRI).

The exploratory objectives of this study are:

- To assess the long-term efficacy of ABBV-8E12 in slowing disease progression and functional impairment in subjects with PSP as measured by exploratory endpoints.
- To assess the long-term effect of ABBV-8E12 on cerebrospinal fluid (CSF) and plasma tau protein levels.
- To assess the long-term effect of ABBV-8E12 on other potential CSF and plasma biomarkers of disease progression.
- To assess body position and gait in a subset of participating subjects using BioStamp digital sensors.

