For the analysis of biomarker data, the actual treatment received will be used rather than the treatment assignment at enrollment. Descriptive statistics will be provided for all scheduled post-baseline times of measurement in Study M15-563, with all subjects who were administered a dose in Study M15-563 included. The descriptive statistics will also be provided for the baseline measurement. For subjects whose treatment in Study M15-562 was one of the ABBV-8E12 doses, the baseline value for Study M15-563 will be the baseline value of Study M15-562. For subjects whose treatment in Study M15-562 was placebo, the baseline value will be the last measurement obtained before the first dose of Study M15-563, which might be the last measurement of Study M15-562 as explained in Section 4.2.

Longer-Term Biomarker Data Set: Only data of subjects whose treatment in Study M15-562 was with one of the ABBV-8E12 dose levels will be included in this data set. The data set will include the data for all scheduled times of measurement of Study M15-563. The baseline value for this data set will be the baseline value of Study M15-562.

6.0 Demographics, Baseline Characteristics, Medical History, and Previous/Concomitant Medications

The data analysis will be conducted among treatment groups defined as Studies M15-562/M15-563: 2000/2000 mg, 4000/4000 mg, placebo/2000 mg, and placebo/4000 mg.

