9.0 Efficacy Analysis

No efficacy analyses will be conducted. Baseline values and change from baseline of the following primary and secondary efficacy variables will be summarized on both ITT data set and Delayed-start data set:

- PSPRS total score
- UPDRS Part II score
- CGI-C score
- SEADL score
- CGI-S score
- PGI-C score
- PSP-SS (composite of items from PSPRS) score

A Figure of mean of PSPRS total score for each visit will be displayed by treatment groups 2000/2000 mg, 4000/4000 mg, placebo/2000 mg, and placebo/4000 mg. This will be conducted on delayed-start data set.

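### SAP 5.1 and 12.2 drop, without a reason, the placebo-start biomarker data and prior-assignment term that Protocol 8.1.3 puts in the tau and MRI dose comparison

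*SAP*

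**What the plan says.** SAP 5.1 names a Longer-Term Biomarker Data Set and restricts it as follows: "Only data of subjects whose treatment in Study M15-562 was with one of the ABBV-8E12 dose levels will be included in this data set". SAP 12.2 uses this data set for its models and describes it so: "All the measurements in this data set were obtained after a subject was on treatment with ABBV-8E12 for 52 weeks or longer". The treatment hypothesis for tau is "The hypothesis of no difference between the main effects of the two ABBV-8E12 dose levels", which "will be tested at significance level 0.050". MRI follows the same route: "For imaging variables, an MMRM analysis corresponding to that described for the tau variables will be performed", with head size as an added covariate for the volumetric variables.

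Protocol 8.1.3 also compares 2000 with 4000 mg, for tau and by extension for volumetric MRI. Its data set holds the two early-start groups and, in addition, both placebo-start groups from M15-563 Week 76 onward. Their time is shifted back 52 weeks so that it counts exposure past the first year. The model carries an effect separating subjects previously on ABBV-8E12 from those previously on placebo. The synopsis (Protocol 1.2, Biomarkers) repeats both features.

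Elsewhere in the SAP, 4.1 keeps slowing of brain atrophy on volumetric MRI as a secondary objective. For tau and volumetric MRI in all four sequence groups, 12.1 says that "descriptive statistics will be provided for each scheduled time of measurement for each treatment group". For the clinical scales, 9.0 states: "No efficacy analyses will be conducted".

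**The concern.** SAP 3.0 says that the SAP elaborates the protocol's methods. Here it removes part of a specified analysis population and a model term without saying so or giving a reason. The section's own exposure criterion does not account for the removal. The dose comparison loses precision that needs no extra data collection, and a reader holding both documents cannot tell which model is the planned one.

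There is also a risk of misreading. The dose test is the only modelled MRI result and it sits beside an objective about slowing, so a non-significant result could be taken as evidence that atrophy was not slowed.

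**Working it through.** **Does the exposure criterion justify the cut?** A placebo-start subject begins ABBV-8E12 on M15-563 Day 1 and at Week 76 has had 76 weeks of it, against the 52 required. On the shifted scale this is 76 − 52 = Week 24. An early-start subject at M15-563 Week 24 has had 52 + 24 = 76 weeks. The two are aligned on exposure, so the criterion gives no ground for exclusion.

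**Do these subjects bear on the dose contrast?** Yes. SAP 4.2 randomizes them 1:1 to 2000 or 4000 mg.

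**Cost in precision (MRI).** The plan gives no figure to reproduce. Inputs:
- 378 randomized in M15-562 (SAP 4.3), taken as the upper limit.
- MRI at Weeks 12, 24 and 52, then six-monthly at 76, 104, 128, 156, 180, 208, 232 and 260 (Protocol 5.1 and Appendix C). Placebo-start Weeks 76 to 260 map to shifted Weeks 24 to 208, all of which are early-start visits.
- Allocation (assumed): the current text gives no M15-562 ratio. At 1:1:1, 378/3 = 126 early-start and 126/2 = 63 placebo-start per dose. At 2:2:1, 378 × 2/5 ≈ 151 and 378/5/2 ≈ 38.
- Dropout (assumed): the same annual loss in all groups, monotone, with retention (1 − loss)^(week/52).
- Within-subject correlation (assumed): compound symmetry, 0.5 to 0.9.

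The model has dose-by-visit means plus the prior-assignment term. The contrast c is the mean over the 11 visits for one dose minus the other. Its variance is c′(ΣX′R⁻¹X)⁻¹c, and the SE ratio is √(variance without placebo-start / variance with).

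| Annual loss | SE ratio, 126 and 63 | SE ratio, 151 and 38 | Placebo-start share of scans (1:1:1; 2:2:1) |
|---|---|---|---|
| 20% | 1.164-1.173 | 1.086-1.090 | 23%; 13% |
| 40% | 1.111-1.123 | 1.058-1.063 | 18%; 10% |
| 60% | 1.056-1.070 | 1.029-1.036 | 12%; 6% |
| none | 1.216-1.224 | 1.114-1.118 | not needed |

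As a check, counting subjects alone gives √(189/126) = 1.22 and √(189/151) = 1.12, which match the no-dropout rows. At 1:1:1 one third of subjects are left out (126/378), but this overstates the loss because they enter only from Week 76. The tau models lose the same subjects; their sparser schedules were not computed.

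**What the dose contrast can show.** If both doses slow atrophy equally, the expected 2000 versus 4000 mg difference is 0 at every visit and the 0.050-level test rejects 5% of the time, whatever the size of the slowing. A null result therefore cannot separate equal benefit from no benefit.

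**The case against.** SAP 5.1 defines its data set explicitly and gives every subject in it one baseline, that of M15-562. Restoring the placebo-start groups brings in a second baseline definition, and those subjects count only if still in the study at Week 76. The precision gained is moderate. All of this stands. But the protocol chose that trade-off knowingly and included the prior-assignment term. Early-start subjects, too, contribute only after completing M15-562 and rolling over. A case for departing from the protocol may exist, but the SAP does not make one.

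A reader might go further and infer that the SAP has stripped the brain-atrophy objective of its analysis, or removed a comparison with untreated or delayed-start subjects. The documents do not support that. The 2000 versus 4000 mg contrast is the protocol's own. The protocol's prior-assignment effect acts on shifted time, so it never gave a same-visit comparison of early with delayed start. Protocol 3.1 puts every M15-563 subject on active drug, so no untreated group exists within the study. The delayed-start analysis in Protocol 8.1.1 covers PSPRS only and is conditional on the M15-562 result. SAP 9.0 openly limits even the primary scale to summaries, and SAP 12.1 describes MRI in all four groups. Nor is the dose test empty: a difference between doses would bear on drug effect. Only a null result is uninformative about slowing.

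**Conclusion.** The SAP departs from Protocol 8.1.3 without explanation, for tau and for volumetric MRI, and its own exposure criterion does not explain the departure. For MRI the cost is an SE of the dose contrast about 6-17% wider at 1:1:1 and 3-9% wider at 2:2:1, over 20-60% annual loss. The upper limits with no dropout are about 22% and 12%. These figures rest on assumed allocation, equal dropout across groups and compound symmetry. The inconsistency itself rests on no assumption.

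The limit on what the dose contrast can say about slowing is a secondary matter of interpretation, inherited from the protocol. It calls for a clarifying sentence. A new early- versus delayed-start model is a choice of scope and is not needed to correct an error.

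**What to change.** 1. In SAP 5.1 and 12.2, restore the placebo-start data from Week 76 on time shifted by 52 weeks, with the M15-563 pre-dose value as baseline for those subjects, and add the prior-assignment term. Keep the early-start-only fit as a sensitivity analysis. The cost is one model term and two baseline definitions; no new data are needed. If the sponsor prefers the narrower data set, the SAP should state the departure and the reason.

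2. Add a sentence to SAP 12.2 saying that the MRI objective is addressed descriptively through 12.1 and that a null dose test is not evidence against slowing.

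3. Optional: a supportive MRI estimate of early versus delayed start. It should be dose-matched (2000/2000 versus placebo/2000, 4000/4000 versus placebo/4000, as in the PSPRS contrasts of Protocol 8.1.1), measured from the common M15-562 baseline, and reported with 95% CIs and no test. By 1.96·√(1/(n₁r) + 1/(n₂r)), with a fraction r = 0.8, 0.6 or 0.4 of subjects scanned, the half-width is 0.34, 0.39 or 0.48 SD of change for 126 versus 63, and 0.40, 0.46 or 0.56 SD for 151 versus 38. The documents give no SD, so these cannot be turned into volumes. The estimate would need a stated exception to SAP 9.0 and to the condition in Protocol 8.1.1, and it depends on M15-562 MRI data whose schedule is not in these documents.
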